SPONSOR INFORMATION

Sponsor Office: CytoDyn, Inc.

[name]

[contact]-Work [contact]-Fax www.cytodyn.com

CONTRACT RESEARCH ORGANIZATION INFORMATION

CONFIDENTIAL Page 4 of 101

PROTOCOL SYNOPSIS

Name of Sponsor/Company:		
CytoDyn, Inc.		
Name of Study Product:		
Leronlimab (PRO 140)		
Protocol Number: Indication:		
CD15 COVID-19	Coronavirus Disease 2019 (COVID-19)	

Title of Study: A Randomized, Double Blind, Placebo Controlled Study to Evaluate the Efficacy and Safety of Leronlimab in Patients Experiencing Prolonged Coronavirus Disease 2019 (COVID-19) Symptoms [Long-Haulers]

Study Center: Up to 5 centers in the United States. Centers must have the capability of implementing appropriate infection-control measures to prevent infection of study staff and others who share the clinical site space.

Planned Number of Subjects: 50 subjects Study Development Phase: Phase 2

Indication for Use: Leronlimab is indicated for treatment of adult patients with prolonged symptoms of Coronavirus disease 2019 (COVID-19).

Objective:

The purpose of this study is to assess the safety and efficacy of leronlimab (PRO 140) administered as weekly subcutaneous injection in subjects experiencing prolonged symptoms (> 12 weeks) of COVID-19.

Study Outcomes (Endpoints):

Primary Outcome (Endpoint) Measure:

Changes from baseline in daily COVID-19-related symptom severity score through Day 56.
 Note: A set of common COVID-19-related symptoms (see patient diary template) will be evaluated daily by the patient regardless of which symptoms a subject had at baseline, as new symptoms may appear following the baseline assessment.

Secondary Outcome (Endpoints) Measures:

 Duration of COVID-19 associated symptoms from start of study treatment (Day 0) based on selfassessment using daily symptom diary.

Duration is defined as number of days when any symptoms scored as

- moderate or severe at baseline are still scored as moderate or severe (i.e., not mild or absent) through Day 56, or
- mild or absent at study entry are scored as mild or worse (i.e., not absent)through Day 56.
- Number of symptom-free days of COVID-19 associated symptoms that were present at the start of study treatment (Day 0) based on self-assessment using daily symptom diary.

CONFIDENTIAL Page 5 of 101

Name of Sponsor/Company:		
CytoDyn, Inc.		
Name of Study Product:		
Leronlimab (PRO 140)		
Protocol Number: Indication:		
CD15_COVID-19	Coronavirus Disease 2019 (COVID-19)	

Symptom-free days are defined as number of days when any symptoms scored as mild, moderate or severe at baseline are scored as absent (or none) through Day 56.

 Progression (or worsening) of COVID-19-associated symptoms through Day 56 compared to baseline.

Progression or symptom worsening is defined as number of days when any symptoms scored as

- moderate at baseline are scored as severe through Day 56.
- mild at baseline are scored as moderate or severe through Day 56.
- absent at baseline are scored as mild, moderate or worse through Day 56.
- Change from baseline in PROMIS® Fatigue Score at Days 28 and 56.
- Change from baseline in PROMIS® Cognitive Function Score at Days 28 and 56.
- Change from baseline in PROMIS® Sleep Disturbance Score at Days 28 and 56.
- Incidence of hospitalization during the treatment phase
- Duration (days) of hospitalization during the treatment phase

Exploratory Outcome (Endpoints) Measures:

- Change from baseline in pulse oxygen saturation (SpO2) at Day 7, 14, 21, 28, 35, 42, 49, and 56.
- Change from baseline in serum cytokine and chemokine levels on Days 28 and 56.
- Change from baseline in CD4+ and CD8+ T cell count on Days 28 and 56.
- Change from baseline in Transgrowth factor beta 1 (TGF beta1) on Days 28 and 56.
- Change from baseline in CRP on Days 28 and 56.
- Change from baseline in CCR5 receptor occupancy on Days 28 and 56.
- To explore biomarkers that may predict and/or act as pharmacodynamic indicators of pharmacologic activity of leronlimab.
- Evaluation of Global Health Assessment at Day 56

Safety Measures:

- Incidence of treatment-related adverse events (TEAEs).
- Incidence and severity of treatment-emergent adverse events (TEAEs).
- Incidence of serious adverse events (SAEs).
- Incidence of TEAEs and SAEs leading to discontinuation of study medication.
- Changes in blood chemistry, hematology and coagulation parameter results.

CONFIDENTIAL Page 6 of 101

Name of Sponsor/Company:		
CytoDyn, Inc.		
Name of Study Product:		
Leronlimab (PRO 140)		
Protocol Number:	Indication:	
CD15_COVID-19	Coronavirus Disease 2019 (COVID-19)	

- Changes in vital signs including temperature, pulse, respiratory rate, systolic and diastolic blood pressure.
- Changes in physical examination results.
- Change in electrocardiogram (ECG) results.

Trial Design:

This is a Phase 2, two-arm, randomized, double blind, placebo controlled multicenter study to evaluate the safety and efficacy of leronlimab (PRO 140) in patients with prolonged symptoms caused by COVID-19. Patients will be randomized to receive weekly doses of 700 mg leronlimab (PRO 140), or placebo. Leronlimab (PRO 140) and placebo will be administered via subcutaneous injection.

The study will have three phases: Screening Period, Treatment Period, and Follow-Up Period.

Screening Period (up to 1 week):

Screening assessments will commence at Visit 1 (V1) after obtaining signed informed consent, and will include review of medical and medication history, eligibility evaluation, vital signs, pulse oxygen saturation, physical examination, electrocardiogram (ECG), clinical symptom score assessment, and laboratory sample collection for routine serum biochemical, hematologic, coagulation, urinalysis, and urine pregnancy (if applicable). These assessments must be conducted within 7 days of the First Treatment Visit (V2).

All subjects who fail to meet eligibility criteria are considered screen failures, and are exited from the study without further evaluation.

Treatment Period (56 Days± allowed windows):

The schedule of visits during Treatment Period is as follows:

- Visit 2 (V2) [first treatment]: Within 1 week of the Screening Visit
- Visit 3 (V3): 3 (±1) days after V2
- Visit 4 (V4) [second treatment]: 7 (±1) days after V2
- Visit 5 (V5): 3 (±1) days after V4
- Visit 6 (V6) [third treatment]: 7 (±1) days after V4
- Visit 7 (V7): 3 (±1) days after V6
- Visit 8 (V8) [fourth treatment]: 7 (±1) days after V6
- Visit 9 (V9): 3 (±1) days after V8
- Visit 10 (V10) [fifth treatment]: 7 (±1) days after V8
- Visit 11 (V11): 3 (±1) days after V10

CONFIDENTIAL Page 7 of 101

Name of Sponsor/Company:		
CytoDyn, Inc.		
Name of Study Product:		
Leronlimab (PRO 140)		
Protocol Number: Indication:		
CD15_COVID-19	Coronavirus Disease 2019 (COVID-19)	

- Visit 12 (V12) [sixth treatment]: 7(±1) days after V10
- Visit 13 (V13): 3 (±1) days after V12
- Visit 14 (V14) [seventh treatment]: 7(±1) days after V12
- Visit 15 (V15): 3 (±1) days after V14
- Visit 16 (V16) [eighth treatment]: 7(±1) days after V14
- Visit 17 (V17) / End of Treatment (EOT) Visit: 7 (±1) days after V16.

Subjects who meet the eligibility criteria will have completed the following evaluations and assessments at V2 prior to treatment: review of any changes in medical and medication history, vital signs, pulse oxygen saturation, physical examination, PROMIS® Fatigue Scale, PROMIS® Cognitive Function, PROMIS® Sleep Disturbance, and blood sample collection for CD4+ and CD8+ T cell count and serum cytokine and chemokine levels and urine pregnancy (if applicable). Subjects will also be given a diary to record all symptoms daily throughout the entire treatment period starting at baseline.

If Visit 2 (V2) takes place on the same day as the Screening Visit (V1), scheduled assessments performed under screening (V1) do not need to be repeated at V2.

Study Drug	Dosage Form	IP concentration	Dosing Frequency and Amount	Route of Administration
DD 0 140	Darantara1		2 injections of PRO 140 (2 X 2	
(700 mg)	Parenteral solution	175 mg/mL	mL/inj.) per week on opposite sides of abdomen	SC injection
			2 injections of placebo (2 X 2	
D11	Parenteral	0 mg/mI	mL/inj.)	SC injection
Placebo	solution	0 mg/mL	per week on opposite sides of abdomen	SC Injection

At V2, subjects will be randomized to receive leronlimab (PRO 140) or placebo which will be administered subcutaneously weekly at V2, V4, V6, V8, V10, V12, V14, and V16.

The following assessments will be performed at V4, V6, V8, V10, V12, V14, V16, and V17(EOT): vital signs, pulse oxygen saturation, physical examination, electrocardiogram (ECG) (V17 only), PROMIS® Fatigue Scale, PROMIS® Cognitive Function, PROMIS® Sleep Disturbance, Global Health Assessment (V17 only), blood sample collection for routine serum biochemical, hematologic, coagulation and urine laboratory assessments (V10 and V17), CD4+ and CD8+ T cell count and serum cytokine and chemokine levels (V10 and V17), assessment for the requirement of hospitalization and patient compliance to daily diary completion will be checked by the site staff.

CONFIDENTIAL Page 8 of 101

Name of Sponsor/Company:		
CytoDyn, Inc.		
Name of Study Product:		
Leronlimab (PRO 140)		
Protocol Number: Indication:		
CD15_COVID-19	Coronavirus Disease 2019 (COVID-19)	

Additionally, telephone or video contact visits will be performed 3 days (±1 day) after each treatment administration visit. The requirement of hospitalization and patient compliance to daily diary completion will be checked during V3, V5, V7, V9, V11, V13, and V15 via telephone.

Adverse events and concomitant medications will be monitored throughout the study.

Follow Up Period (4 weeks after EOT± allowed windows)

Follow-up visit (V18) will be performed at 4 weeks after the End of Treatment (EOT) visit. The following assessments will be performed at V18: vital signs, physical examination, pulse oxygen saturation, blood sample collection for immunophenotypic biomarker analysis, assessment for the requirement of hospitalization, review of adverse events and concomitant medications.

Note: During visits conducted at the study clinic, subjects and site personnel will use appropriate protective gear (e.g., masks, gloves) to prevent the spread of the infection.

Duration of Treatment:

Screening Period (Screening to Baseline): Up to 7 days (1 Week)

Treatment Period: 56 Days

Follow-Up Period: 28 Days (4 weeks)

Total Study Duration: 91 Days

Inclusion Criteria:

- 1. Male or female adult \geq 18 years of age at time of enrollment.
- 2. Prior confirmed COVID-19 diagnosis by standard RT-PCR assay or equivalent testing
- 3. Clinical Symptom Score of ≥6 AND at least two symptoms of moderate or higher severity as listed below at the time of Screening and currently experiencing two or more of the following symptoms consistent with COVID-19 infection for a prolonged period of time (>12 weeks).

Clinical symptoms include the following:

- Respiratory symptoms such as cough, sore throat, stuffy or runny nose, shortness of breath (difficulty breathing), tightness of chest..
- Neurological symptoms such as difficulty in concentration (brain fog), sleep disturbance/insomnia, headache, dizziness, anxiety, tingling or numbness, loss of sense of smell or taste.
- Cardiovascular and Gastrointestinal symptoms such as feeling of fast heartbeat, nausea, vomiting, diarrhea.

CONFIDENTIAL Page 9 of 101

Name of Sponsor/Company:		
CytoDyn, Inc.		
Name of Study Product:		
Leronlimab (PRO 140)		
Protocol Number: Indication:		
CD15_COVID-19	Coronavirus Disease 2019 (COVID-19)	

- Musculoskeletal symptoms such as muscle aches/cramps, muscle weakness, joint pain/swelling.
- General immune response symptoms such as fatigue (low energy or tiredness), chills or shivering, feeling hot or feverish, or exertional malaise (feeling of discomfort, illness, or lack of well-being after physical activity or mental stress).

Note: Clinical Symptom Score is obtained from the patient diary (refer to Appendix 1 for scoring instructions).

4. Electrocardiogram (ECG) with no clinically significant findings as assessed by the Investigator.

Note: Below are the examples of clinically significant and non-clinically significant ECG abnormalities:

- ECG findings indicative of acute myocardial infarction or acute ischemic changes would be considered clinically significant abnormalities.
- ECG finding such as atrial fibrillation, atrial flutter, paced rhythms in individuals who have undergone permanent pacemaker placement, evidence of prior infarction, unchanged stable conduction abnormalities e.g. right bundle branch block, or any other finding which does not significantly impact mortality would be considered non-clinically significant findings and subjects with these abnormal findings would be allowed to enroll in the study.
- 5. Subject (or legally authorized representative) provides written informed consent prior to initiation of any study procedures.
- 6. Men and women of childbearing potential and their partner must agree to use two medically accepted methods of contraception (e.g., barrier contraceptives [male condom, female condom, or diaphragm with a spermicidal gel], hormonal contraceptives [implants, injectables, combination oral contraceptives, transdermal patches, or contraceptive rings], or one of the following methods of birth control (intrauterine devices, bilateral tubal occlusion, or vasectomy) or must practice complete sexual abstinence for the duration of the study (excluding women who are not of childbearing potential and men who have been sterilized).
- 7. Females of child-bearing potential must have a negative urine pregnancy test at Screening Visit and prior to receiving the first dose of study drug; and Male participants must agree to use contraception and refrain from donating sperm for at least 90 days after the last dose of study intervention.
- 8. Subject is willing and able to comply with scheduled visits, drug administration plan, laboratory tests, other study procedures and study restrictions

Exclusion Criteria:

Exhibiting signs of moderate or severe pulmonary disease (such as COPD, asthma, or pulmonary fibrosis)

CONFIDENTIAL Page 10 of 101

Name of Sponsor/Company:		
CytoDyn, Inc.		
Name of Study Product:		
Leronlimab (PRO 140)		
Protocol Number: Indication:		
CD15_COVID-19	Coronavirus Disease 2019 (COVID-19)	

- 2. Ongoing requirement of oxygen therapy
- 3. Pulse oxygen saturation (SpO2) of <94% on room air at the time of screening
- 4. History of splenectomy
- 5. Liver cirrhosis or patient showing signs of clinical jaundice at the time of screening
- 6. Chronic kidney disease stage 4 or requiring dialysis at the time of screening
- 7. NYHA Class III or IV congestive heart failure (CHF)
- 8. Exhibiting signs of uncontrolled hypo-or hyper-thyroidism at the time of Screening
- 9. Uncontrolled rheumatologic disorders at the time of screening
- 10. History of organ transplantation or are candidates for organ transplantation at the time of screening
- 11. History of Chronic Fatigue Syndrome prior to COVID-19 infection
- 12. History of fibromyalgia prior to COVID-19 infection
- 13. History of major psychiatric disorder including bipolar disorders, schizophrenia, schizoaffective disorder, major depression. Patients with major depression can be enrolled if patient has had no episode within the past year or is considered in remission or controlled by treatment.
- 14. Any malignancy within the past 5 years, excluding successfully treated basal cell carcinoma or squamous cell carcinoma without evidence of metastases.
- 15. Any other clinically significant serious systemic diseases which would interfere with study conduct or study results interpretation per the Investigator.
- 16. Treatment with immunosuppressive or immunomodulatory medications within 5 half-lives prior to screening. Patients on replacement therapy for adrenal insufficiency will be allowed. Patients on stable (> 3 months) low dose corticosteroid ≤ 5 mg Prednisone will be allowed.
- 17. History of allergic reactions attributed to compounds of similar chemical or biologic composition to leronlimab (PRO 140) are not eligible
- 18. Ongoing use of CCR5 antagonist
- 19. Inability to provide informed consent or to comply with test requirements
- 20. Consideration by the investigator, for safety reasons, that the subject is an unsuitable candidate to receive study treatment
- 21. Pregnancy or breast feeding

CONFIDENTIAL Page 11 of 101

Name of Sponsor/Company:		
CytoDyn, Inc.		
Name of Study Product:		
Leronlimab (PRO 140)		
Protocol Number: Indication:		
CD15_COVID-19	Coronavirus Disease 2019 (COVID-19)	

22. Participating in another study for an investigational treatment

Statistical Considerations:

Sample Size Determination and Rationale

A total of 50 subjects will be randomized 1:1 in this study. The sample size is based on clinical judgment. No statistical power calculation is used to establish the sample size for this exploratory study.

Analysis Populations

The **Modified Intent-to-Treat (mITT) population** is defined as the set of subjects who have received at least one dose of study treatment (leronlimab or placebo). This population will be used for the analysis of efficacy parameters or measurements.

The **Per Protocol (PP) population** is defined as the set of subjects who meet the mITT Population requirements and were not associated with any major protocol violations. This population will be identified before the database lock.

The **Safety Population** will include all subjects who have received one dose of study treatment (leronlimab or placebo). This population will be used for the analysis of safety parameters or measurements.

Analysis Methods

Descriptive statistics (n, mean, standard deviation, median, minimum, and maximum) will be calculated for continuous variables. Frequencies and percentages will be presented for categorical variables.

CONFIDENTIAL Page 12 of 101

[figure not shown]
[figure not shown]

[figure not shown]
TABLE OF CONTENTS

PRO	DTOCOL S	SYNOPSIS	5
TAB	BLE OF CO	ONTENTS	13
List	of Tables		18
List	of Figures .		19
List	of Abbrevia	ations	20
1 I	NTRODU	CTION AND BACKGROUND	22
1.1.	Statement	t of Intent	22
1.2.	Backgrou	and of the Disease	22
1.3.	Leronlima	ab (PRO 140)	23
1.4.	Summary	of Prior Pre-Clinical and Clinical Studies	23
	1.4.1.	Pre-Clinical Studies with PRO 140	23
	1.4.2.	Clinical Studies with PRO 140	24
1.5.	Study Rat	tionale	35
1.6.	Risks / Be	enefits Assessment	37
2. S	STUDY OB	BJECTIVES	39
3. S	STUDY DE	SIGN	40
3.1.	Study Cer	nter	41
3.2.	Study Pop	pulation	41
3.3.	Eligibility	y Criteria	41
	3.3.1.	Inclusion Criteria	41
	3.3.2.	Exclusion Criteria	42
4. S	STUDY SC	HEDULE	44
4.1.	Screening	g Phase	49
	4.1.1.	Screening Visit (V1)	49
4.2.	Treatmen	t Phase	50

[figure not shown]

	4.2.1.	Visit 2 (V2)	50			
	4.2.2.	Visits 3, 5, 7, 9, 11, 13, and 15 (V3, V5, V7, V9, V11, V13, and V15)	51			
	4.2.3.	Visits 4, 6, 8, 10, 12, 14, and 16 (V4, V6, V8, V10, V12, V14, and V10	6)51			
	4.2.4.	End of Treatment – EOT (V17)	52			
4.3.	Follow-U	Up Phase	53			
	4.3.1.	Visit 18	53			
4.4.	Unsched	uled Visits	53			
5. S	UBJECT	COMPLETION, WITHDRAWAL AND CRITERIA FOR STOPPING	NG THE			
S	TUDY		54			
5.1.	Subject (Completion	54			
5.2.	Early Sto	opping Rules	54			
5.3.	Remova	l of Subjects from Study Treatment and/or Study as a Whole	54			
5.4.	Data Col	llected from Withdrawn Subjects	55			
5.5.	Screen F	ailures	55			
6. S	TUDY TI	REATMENT	56			

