Window Period		Within 7 days of the Screening Visit	3(±1) days after V2	7(±1) days after V2	3(±1) days after V4	7(±1) days after V4	3(±1) days after V6	7(±1) days after V6	3(±1) days after V8	7(±1) days after V8	3(±1) days after V10	7(±1) days after V10	3(±1) days after V12	7(±1) days after V12	3(±1) days after V14	7(±1) days after V14	7(±1) days after V16	28(±3) days after V17
Urine Pregnancy Test [12]	X	X								X							X	
Urinalysis [13]	X									X							X	
CD4+ and CD8+ T cell count		X								X							X	
Serum cytokine and chemokine levels [14]		X								X							X	
CCR5 Receptor Occupancy		X								X							X	
Immunophenotypic Biomarker Analysis		X								X							X	X
Randomization [15]		X																
PRO 140 (700 mg) or Placebo Administration		X		X		X		X		X		X		X		X		
Assessment for Requirement of Hospitalization			X	X	х	X	х	X	x	X	х	X	х	х	X	X	X	x
Concomitant Medications	X	X	X	X	X	X	X	X	X	X	X	X	X	X	X	X	X	X
Adverse Events			X	X	X	X	X	X	X	X	X	X	X	X	X	X	X	X

- [1] Informed consent must be obtained prior to patient participation in any protocol-related activities that are not part of routine care.
- [2] Initial evaluation of patient eligibility will be performed by Investigator.
- [3] Medical history and current therapies (medications and non-medications).
- [4] Symptom-directed physical examination
- [5] Pre-treatment and post-treatment vital signs and SpO2 will be recorded at V2. Post-treatment vital signs and SpO2 will be recorded at V4, V6, V8, V10, V12, V14, and V16. Vital Signs will include blood pressure, heart rate, respiration rate, temperature, weight, and height. (Note: Height will be measured only at V1).
- [6] Symptom Score will be assessed for patient eligibility based on symptom score for following symptoms consistent with COVID-19 as a result of confirmed SARS-CoV-2 infection for a prolonged period of time (>12 weeks) (Total Clinical Symptom Score of ≥6 with at least two symptoms of moderate or higher severity at the time of Screening (at V1) and prior to Randomization (at V2)
- [7] Patients will be asked to complete a daily diary during the treatment phase to record symptoms.
- [8] All three questionnaires, PROMIS® Fatigue Scale, PROMIS® Cognitive Function, and PROMIS® Sleep Disturbance will be evaluated before study drug administration.
- [9] Hemoglobin, Hematocrit (HCT), Red Blood Cells (RBC), White Blood Cells (WBC) with total and differential count, Absolute Neutrophil Count (ANC) and platelets.
- [10] Biochemistry

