4.2.4. End of Treatment – EOT (V17)

The last visit during the treatment phase will be considered at the End of Treatment (EOT) visit. The assessments performed at this visit will include:

- Physical examination (see Section 7.5);
- Vital Signs (see Section 7.6),
- Pulse oxygen saturation (SpO2) (see Section 7.10);
- 12-lead electrocardiogram (see Section 7.11);
- Patient Symptom Diary (see Section 7.15);

Note: Patient compliance to daily diary completion will be checked by site staff.

- PROMIS® Fatigue Scale (see Section 7.16);
- PROMIS® Cognitive Function (see Section 7.17);
- PROMIS® Sleep Disturbance (see Section 7.18);
- Global Health Assessment (see Section 7.19);
- Collection of laboratory specimens (see Section 7.8) for
 - Complete blood count;

CONFIDENTIAL Page 52 of 101

- Biochemistry;
- Coagulation indices;
- O Urine pregnancy test, for female subjects of childbearing potential;
- Urine sample for urinalysis parameters;
- o CD4+ and CD8+ T cell count;
- Serum cytokine and chemokine levels;
- o CCR5 receptor occupancy; and
- Immunophenotypic biomarker analysis.
- Assessment for the requirement of hospitalization (see Section 7.12);
- Prior and concomitant medications assessment (see Section 7.7); and
- Review of adverse events (see Section 9).

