3.2 Secondary Endpoints

The secondary endpoints for the study are:

• Duration of COVID-19 associated symptoms from start of study treatment (Day 0) based on self-assessment using daily symptom diary

Duration is defined as number of days when any symptoms scored as

- 2 or 3 at baseline are still scored as 2 or 3 (i.e., not 0 or 1) through Day 56, or
- 1 or 0 at study entry are scored as 1 or worse (i.e., not 0) through Day 56.
- Number of symptom-free days of COVID-19 associated symptoms that were present at the start of study treatment (Day 0) based on self-assessment using daily symptom diary *Symptom-free days are defined as number of days when any symptoms scored as* 1, 2 or 3 at baseline are still scored as 0 through Day 56.
- Progression (or worsening) of COVID-19-associated symptoms through Day 56 compared to baseline

Progression or symptom worsening is defined as number of days when any symptoms scored as

- 2 at baseline are still scored as 3 through Day 56, or
- 1 at baseline are still scored as 2 or 3 through Day 56, or
- 0 at study entry are scored as worse (i.e., not 0) through Day 56.
- Change from baseline in PROMIS® Fatigue Score at Days 28 and 56
- Change from baseline in PROMIS® Cognitive Function Score at Days 28 and 56
- Change from baseline in PROMIS® Sleep Disturbance Score at Days 28 and 56
- Incidence of hospitalization during the treatment phase
- Duration (days) of hospitalization during the treatment phase

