7.3 Handling of Missing Data

Every effort will be made to obtain required data at each scheduled evaluation from all subjects who have been randomized to minimize missing data. Missing data will not be imputed.

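### Three secondary endpoints are raw day counts over diaries of unequal length: the diary stops at V17, which can fall on Day 48 to 64, and earlier still in subjects who leave

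*Combined protocol and SAP*

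**What the plan says.** The synopsis, protocol section 4 and SAP 2.2 list the same schedule. It starts from V2 as Day 0 ("Visit 4 (V4) [second treatment]: 7 (±1) days after V2"), runs through steps such as "Visit 10 (V10) [fifth treatment]: 7 (±1) days after V8", and closes with "Visit 17 (V17) / End of Treatment (EOT) Visit: 7 (±1) days after V16". The only acknowledgement of cumulative tolerance is the label "Treatment Period (56 Days± allowed windows". Protocol Table 4-2 and SAP Table 2-1 print fixed days (Day 28, Day 56) above the same chained windows.

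The diary belongs to the treatment phase. Note 7 to Table 4-2 reads "Patients will be asked to complete a daily diary during the treatment phase to record symptoms", and protocol 4.2.4 ends that phase at V17: "The last visit during the treatment phase will be considered at the End of Treatment (EOT) visit". V18 has no diary assessment (protocol 4.3.1).

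SAP 3.2 and 8.2.2 define three secondary endpoints as numbers of days, for example symptoms scored "2 or 3 at baseline are still scored as 2 or 3 (i.e., not 0 or 1) through Day 56" for duration. They are compared by a non-parametric method or rank ANCOVA. SAP 7.3 says "Missing data will not be imputed". Protocol 8.9.3 says the opposite for efficacy data: multiple imputation, with details left to the SAP.

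**The concern.** A count of days is comparable between subjects only if all were observed for the same number of days, or if the analysis allows for the difference. Here the number of diary days depends on when V17 happens or when the subject leaves, and nothing in the SAP adjusts for it. In a rank analysis a truncated diary ranks as short symptom duration and also as few symptom-free days, so the endpoints partly measure observation time.

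The SAP recognises this kind of problem elsewhere. For duration of hospitalization, section 7.7.4 gives deaths the worst rank. There is no counterpart for symptom days.

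**Working it through.** **Step 1: reproduce the nominal day.** From V2 through V4, V6, V8, V10, V12, V14 and V16 to V17 there are 8 intervals. 8 × 7 = 56, which agrees with the stated Day 56.

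**Step 2: allowed range.** Each interval may be 6 to 8 days.
- V17: 8 × 6 = 48 to 8 × 8 = 64.
- V10 (nominal Day 28): 4 × 6 = 24 to 4 × 8 = 32.
- V16 (nominal Day 49): 7 × 6 = 42 to 7 × 8 = 56.

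A V17 on Day 48 leaves 56 − 48 = 8 diary days uncollected, or 8/56 = 14.3%. A V17 after Day 56 loses none, because the counts stop at Day 56.

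**Step 3: likely size of the drift.** The documents give no distribution of visit timing, so this step rests on assumptions. Take the eight deviations as independent, each −1, 0 or +1 day, and convolve them exactly. Diary days lost = max(0, 56 − day of V17).

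| Assumed probabilities of −1 / 0 / +1 | SD of V17 day | V17 before Day 56 | At least 3 days early | Exactly Day 48 | Mean days lost |
|---|---|---|---|---|---|
| 1/3, 1/3, 1/3 | 2.31 | 41.6% | 14.1% | 0.00015 | 0.91 |
| 0.2, 0.6, 0.2 | 1.79 | 38.9% | 7.9% | 0.0000026 | 0.70 |
| 0.1, 0.8, 0.1 | 1.26 | 33.4% | 2.3% | 0.00000001 | 0.47 |

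The mean loss is 0.47/56 = 0.8% to 0.91/56 = 1.6% of the diary.

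**Step 4: chance difference between arms from drift.** Under equal probabilities the lost days have SD 1.35. With 25 subjects per arm, the SE of the difference in mean loss is 1.35 × √(2/25) = 0.38 day. Its expected value is zero if timing does not depend on arm.

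**Step 5: early leavers, for comparison.** Protocol 5.3 allows voluntary withdrawal and also removes subjects from the study after two consecutive missed doses. Suppose, for illustration, that a diary ends on Day 20 and counting runs from Day 1.
- Days lost: 56 − 20 = 36.
- With symptoms every day, the leaver scores 20. A completer with symptoms on half the days scores 28. The leaver ranks better on duration despite symptoms on 100% of observed days against 50%.
- With no symptoms on any observed day, the leaver scores 20 symptom-free days against 28 for the same completer, and ranks worse despite 100% against 50%.
- One such leaver in an arm of 25 lowers that arm's mean observable days by 36/25 = 1.44. That exceeds the mean drift loss in every row of the table.

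The planned test uses ranks, so these means show the relative size of the two sources and not the effect on the test statistic.

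**The case against.** The strongest reply is about size and direction. Day 48 needs all eight intervals to run short. Under equal probabilities, losing five or more days has probability 157/6561 = 2.4%, about one subject in 50. Sites that schedule to the printed nominal days would correct drift and reduce this further. Dosing is blinded and both arms share the same windows, so drift should mainly add noise. All of that stands.

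A reader might infer from the Day 48 limit that about 14% of diary data is typically at risk, or that the windows favour leronlimab. The documents support neither. The 14.3% is an extreme of the allowed range, nothing links visit timing to arm, and the same truncation moves symptom duration and symptom-free days in opposite directions.

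It can also be said that dropout is a missing-data question and that protocol 8.9.3 already answers it with multiple imputation, which could fill uncollected days up to Day 56. That would help if the rule were in force. But SAP 7.3 says the reverse, and the SAP contains none of the imputation details that the protocol defers to it. Until the two are reconciled, the handling of these days is unsettled.

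A further inference would be that PROMIS and laboratory values should be reassigned to Day 28 and Day 56 by calendar day. The schedule does not support this. After V2, the cytokine, T-cell and receptor-occupancy samples are taken on treatment only at V10 and V17 (protocol 7.8), so there is nothing to choose between. PROMIS is completed before dosing. A subject running one day late each week has V16 on Day 56, before the eighth dose, so remapping could mix values after seven doses with values after eight. The 7-day recall of the PROMIS forms also makes a drift of one or two days matter little.

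**Conclusion.** The concern holds for the three day-count secondary endpoints. The Day 48 to 64 range is exact arithmetic from the stated windows. The truncation follows from a diary that ends at V17 combined with raw counts that the SAP neither imputes nor rescales.

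Drift alone is small: a mean loss of about 0.5 to 0.9 day of 56, assuming independent deviations with the probabilities shown. The more serious exposure is early leaving. It can cost tens of diary days per subject, and the blind does not guarantee that it is balanced between arms. How many subjects will leave is not known from the documents, so no bias is estimated here.

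This merits correction before database lock. It does not undermine the design of an exploratory 50-subject trial, and no effect on the primary endpoint has been worked out.

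**What to change.** Leave the visit and dosing windows unchanged.

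1. **Protocol 7.15:** state that the diary continues through calendar Day 56 from first dose, whatever the date of V17, and after stopping treatment where follow-up is permitted.
2. **SAP 3.2 and 8.2.2:** fix one counting interval through Day 56, stating whether Day 0 counts. Analyse each day-count endpoint as a proportion of days with a diary entry.
3. **Sensitivity analysis:** add one for early leavers. A proportion puts subjects on a common scale, but it treats the observed days as representative and does not remove informative dropout.
4. **Missing-data rule:** reconcile SAP 7.3 with protocol 8.9.3.
5. **PROMIS and laboratory values:** keep them at V10 and V17 and report the actual study day.

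The cost is SAP text, a protocol wording change that needs IRB approval under protocol 11.3, and at most 8 extra diary days for an in-window early finisher. No diary check is scheduled after V17, so completion of those last days would rest on the subject unless the sponsor adds a contact.
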